13.2.7.4 Serious Adverse Event

If any AEs are serious, as defined by the FDA Code of Federal Regulations (CFR), Title 21, special procedures will be followed. All SAEs will be reported to the Sponsor or designee via fax or e-mail within 24 hours of first awareness of the event, whether or not the serious event(s) are deemed drug-related. All serious event reporting will adhere to 21 CFR 312.32 for Investigational New Drugs (IND) and to the Guidance for Industry and Investigators: Safety Reporting Requirements for INDs and BA/BE, dated December 2012. Any event that meets the criteria of a suspected unexpected serious adverse reaction (SUSAR) will be reported to the IRB/IEC according to site/CRU policy by the Investigator (or designee) and to regulatory authorities by the Sponsor (or Sponsor designee) according to regulatory authority requirements. Refer to Reference Safety Information (RSI) in the current IB for expected adverse reactions.

A SAE is any AE or suspected adverse reaction that in the view of either the PI (or designee) or Sponsor, results in any of the following outcomes: Death, a life-threatening AE, inpatient hospitalization or prolongation of existing hospitalization, a persistent or significant incapacity or disability, or a congenital anomaly/birth defect. Important medical events that may not result in death, be life-threatening, or require hospitalization may be considered serious when, based upon appropriate medical judgment, they may jeopardize the patient or subject and may require medical or surgical intervention to prevent one of the outcomes listed in the above definition.

Examples of such medical events include allergic bronchospasm requiring intensive treatment in an emergency room or at home, blood dyscrasias or convulsions that do not result in inpatient hospitalization, or the development of drug dependency or drug abuse.

Life-threatening is defined as an AE or suspected adverse reaction that in the view of the PI (or designee) or Sponsor, places the patient or subject at immediate risk of death. It does not include an AE or suspected adverse reaction that, had it occurred in a more severe form, might have caused death.

All SAEs must be reported on a SAE Report Form provided by Loxo Oncology and sent by fax or e-mail to the Sponsor listed in [Section 3](#) within 24 hours of first awareness of the event.

When using the SAE efax (+ 1 [contact]) a cover page including study identification number and study drug product (i.e., LOXO-292) is required. Alternatively, an email can be sent to [contact].

The PI is not obligated to actively seek information regarding the occurrence of new SAEs beginning after EOS. However, if the PI learns of such an SAE, and that event is deemed associated with the use of study drug, he/she should promptly document and report the event.

The PI will be requested to supply detailed information as well as follow-up regarding the SAE. Although not considered an AE per se, the Sponsor must be notified of any subject or subject's partner who becomes pregnant during the study at any time between Screening until 90 days after the last administration of study drug.

13.3 Pharmacokinetic Assessments

13.3.1 Blood Sampling and Processing

For all subjects, blood samples for the determination of repaglinide and LOXO-292 will be collected at scheduled time points as delineated in the Study Events Flow Chart ([Section 6](#)).

Instruction for blood sampling, collection, processing, and sample shipment will be provided separately.

Blood collections in Periods 1 and 2 performed outside of the sample collection windows defined in the Study Events Flow Chart ([Section 6](#)) will be considered deviations.

* Where a scheduled blood draw coincides with a scheduled dosing, the blood draw is to be taken prior to dosing

13.3.2 Pharmacokinetic Parameters

PK parameters for plasma repaglinide in Period 1, Day 1, and Period 2, Day 10, will be calculated as follows, as appropriate:

AUC0-t:	The area under the concentration-time curve, from time 0 to the last observed non-zero concentration, as calculated by the linear trapezoidal method.
AUC0-inf:	The area under the concentration-time curve from time 0 extrapolated to infinity. AUC0-inf is calculated as the sum of AUC0-t plus the ratio of the last measurable plasma concentration to the elimination rate constant.
AUC%extrap:	Percent of AUC0-inf extrapolated, represented as $(1 - AUC0-t/AUC0-inf) * 100$.
CL/F:	Apparent total plasma clearance after oral (extravascular) administration, calculated as Dose/AUC0-inf.
Cmax:	Maximum observed concentration.
Tmax:	Time to reach Cmax. If the maximum value occurs at more than one time point, Tmax is defined as the first time point with this value.
Kel:	Apparent first-order terminal elimination rate constant calculated from a semi-log plot of the plasma concentration versus time curve. The parameter will be calculated by linear least-squares regression analysis using the maximum number of points in the terminal log-linear phase (e.g., three or more non-zero plasma concentrations).
t½:	Apparent first-order terminal elimination half-life will be calculated as $0.693/Kel$.
Vz/F:	Apparent volume of distribution during the terminal elimination phase after oral (extravascular) administration, calculated as $(Dose/AUC0-inf) \times Kel$.

PK parameters for plasma LOXO-292 in Period 2, Day 1 and Day 10, will be calculated as follows after the morning dose, as appropriate:

AUC0-t:	The area under the concentration-time curve, from time 0 to the last observed non-zero concentration, as calculated by the linear trapezoidal method (Day 1).
AUC0-12:	The area under the concentration-time curve, from time 0 to the 12 hour timepoint, as calculated by the linear trapezoidal method (Day 1).
AUCtau:	The area under the concentration-time curve during a dosing interval (tau) at steady state (Day 10).

CL,ss/F:	Apparent total plasma clearance after oral (extravascular) administration, calculated as Dose/AUC _{tau} (Day 10).
Cmax:	Maximum observed concentration (Day 1).
Cmax,ss:	Maximum observed concentration at steady-state (Day 10).
Ctrough:	Concentration observed at the end of the dosing interval (Days 2 to 10).
Tmax:	Time to reach Cmax. If the maximum value occurs at more than one time point, Tmax is defined as the first time point with this value (Day 1).
Tmax,ss:	Time to reach Cmax,ss. If the maximum value occurs at more than one time point, Tmax,ss is defined as the first time point with this value (Day 10).

No PK parameters will be calculated for subjects with 2 or fewer consecutive time points with detectable concentrations.

Individual and mean plasma concentration time curves (both linear and log-linear) will be included in the final Clinical Study Report.

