9.2 Endpoints

Pharmacokinetics:

The primary PK endpoints for repaglinide will include, as appropriate, AUC0-t, AUC0-inf, AUC%extrap, Cmax, Tmax, Kel, t½, CL/F, and Vz/F.

The secondary PK endpoints for LOXO-292 will include, as appropriate following the morning dosing, AUC0-12, AUC0-t, Cmax, and Tmax on Day 1 of Period 2 and AUCtau, Cmax,ss, Ctrough, Tmax,ss, and CL,ss/F on Day 10 of Period 2.

Safety:

Safety endpoints will include 12-lead ECGs, physical examinations, vital signs, glucose monitoring, clinical laboratory tests, and AEs.

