6.4 Pharmacokinetic Concentrations

Plasma concentrations of repaglinide and LOXO-292 as determined at the collection times and per the bioanalytical methods described in Section 6.1 and Section 6.2, respectively, will be used for the calculation of the plasma repaglinide and LOXO 292 PK parameters.

6.5 Noncompartmental Pharmacokinetic Analysis and Parameter Calculation for Repaglinide and LOXO-292

The appropriate noncompartmental PK parameters will be calculated from the plasma repaglinide and LOXO-292 concentration-time data using Phoenix® WinNonlin® Version 7.0 or higher. Actual sample collection times will be used in the calculations of the PK parameters. The calculation of the actual time for repaglinide will be in respect to the dose administration time of repaglinide on Day 1 of Period 1 and Day 10 of Period 2. The calculation of the actual time for LOXO-292 will be in respect to the administration time of the morning LOXO-292 dose on Days 1 and 10 in Period 2. All PK parameters included in the protocol are listed in Tables 6.1, 6.2, and 6.3 below, and are defined as appropriate for study design.

Table 6.1. Noncompartmental Pharmacokinetic Parameters to be Calculated for Repaglinide

Label to be Used in the Text, Tables and Figures	Definition	Method of Determination
AUC0-t	Area under the concentration-time curve from time 0 to the time of the last observed non-zero concentration	Calculated using the Linear Trapezoidal with Linear Interpolation Method
AUC0-inf	Area under the concentration-time curve from time 0 extrapolated to infinity	Calculated as AUC0-t + (Clast/Kel) where Clast is the last observed/measured concentration
AUC%extrap	Percent of AUC0-inf extrapolated	Calculated as (1- AUC0-t/AUC0-inf)*100
Cmax	Maximum observed concentration	Taken directly from bioanalytical data
Tmax	The time to reach Cmax. If the maximum value occurs at more than one time point, Tmax is defined as the first time point with this value	Taken from clinical database as the difference in the time of administration and the time of the blood draw which is associated with the Cmax.
Kel	Apparent terminal elimination rate constant; represents the fraction of drug eliminated per unit time	Calculated as the negative of the slope of a linear regression of the log(concentration)-time for all concentrations >LLOQ during the terminal elimination phase
t½	Apparent first-order terminal elimination half-life	Calculated as 0.693/Kel

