CL/F	Apparent total plasma clearance after oral (extravascular) administration	Calculated as Dose/(AUC0-inf)
Vz/F	The apparent volume of distribution during the terminal elimination phase after extravascular administration	Calculated as Dose/(AUC0-inf x Kel)

Table 6.2. Single-dose Noncompartmental Pharmacokinetic Parameters to be Calculated for LOXO-292 on Day 1

Label to be Used in the Text, Tables and Figures	Definition	Method of Determination
AUC0-12	Area under the concentration-time curve from time 0 to 12 hours	Calculated using the Linear Trapezoidal with Linear Interpolation Method
AUC0-t	Area under the concentration-time curve from time 0 to the time of the last observed non-zero concentration	Calculated using the Linear Trapezoidal with Linear Interpolation Method
Cmax	Maximum observed concentration	Taken directly from bioanalytical data
Tmax	The time to reach Cmax. If the maximum value occurs at more than one time point, Tmax is defined as the first time point with this value	Taken from clinical database as the difference in the time of administration and the time of the blood draw which is associated with the Cmax.

Table 6.3. Multiple-dose Noncompartmental Pharmacokinetic Parameters to be Calculated for LOXO-292 on Day 10

Label to be Used in the Text, Tables and Figures	Definition	Method of Determination
AUCtau	Area under the concentration-time curve during a dosing interval, tau, at steady state Will be calculated after the morning dose, where tau is defined as 12 hours	Calculated using the Linear Trapezoidal with Linear Interpolation Method
Cmax,ss	The maximum observed concentration at steady state, following the morning dose	Taken directly from bioanalytical data
Ctrough*	Concentration observed at the end of a dosing interval Dosing interval is defined as 12 hours following the 2 nd dose on Days 1, 2, 3, 4, 5, 6, 7, 8, and 9 (corresponding to pre-morning dose samples collected on Days 2, 3, 4, 5, 6, 7, 8, 9, and 10)	Taken directly from bioanalytical data at any given time point

Label to be Used in the Text, Tables and Figures	Definition	Method of Determination
Tmax,ss	The time to reach Cmax at steady state, following the morning dose	Taken from clinical database as the difference in the time of administration and the time of the blood draw which is associated with the Cmax.
CL,ss/F	Apparent total body clearance estimated at steady state after oral/extravascular administration	Calculated as Dose/AUC _{tau,ss}

CCI

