8. SUMMARY OF CHANGES FROM PROTOCOL-PLANNED ANALYSIS

The analyses described in this SAP are aligned with those analyses described in the protocol.

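### Does the misplaced Kel in the protocol's formula for repaglinide Vz/F put any reported result at risk?

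*Protocol*

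**What the plan says.** Protocol Section 13.3.2 lists the repaglinide parameters with their formulas. Clearance is the "Apparent total plasma clearance after oral (extravascular) administration, calculated as Dose/AUC0-inf". Vz/F is the "Apparent volume of distribution during the terminal elimination phase after oral (extravascular) administration, calculated as" (Dose/AUC0-inf) × Kel, with the bracket closed before Kel.

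SAP Table 6.1 (Section 6.5) gives the same parameter as "Calculated as Dose/(AUC0-inf x Kel"), with Kel inside the denominator. The same table describes Kel as the "Apparent terminal elimination rate constant; represents the fraction of drug eliminated per unit time".

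SAP Section 8 reports no departures: "The analyses described in this SAP are aligned with those analyses described in the protocol".

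The status of Vz/F varies within the protocol. Section 9.2 reads "The primary PK endpoints for repaglinide will include, as appropriate, AUC0-t, AUC0-inf, AUC%extrap, Cmax, Tmax, Kel, t½, CL/F, and Vz/F". Section 8.2.3, which gives the rationale for the primary endpoints, names only AUC0-t, AUC0-inf and Cmax. Section 14.3 hands detailed methodology to the SAP and allows it to modify the protocol's plans, but asks for an amendment if a primary endpoint definition or its analysis undergoes a major modification.

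**The concern.** The two documents give different formulas for one parameter, and only one of them yields a volume. The SAP says it matches the protocol, so nobody reading Section 8 would learn of the difference.

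The parameter is not idle. Vz/F is tabulated for Treatments A and B in SAP Table 11-2, next to CL/F and t½, and a reader would look at the three together to judge whether LOXO-292 alters clearance or distribution. The protocol expects inhibition of CYP2C8 (Section 14.1), so clearance may fall. Under the protocol's formula that fall would enter twice, once through CL/F and once through Kel, and would show as a large drop in apparent volume even if distribution had not changed. Section 9.2 also places Vz/F among the primary PK endpoints, which suggests that the amendment rule in Section 14.3 might apply.

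**Working it through.** There is no planned figure to reproduce here. The check is of units and algebra.

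**Inputs**
- CL/F = Dose/AUC0-inf (Protocol 13.3.2; SAP Table 6.1).
- Kel is a rate, in 1/time, and t½ = 0.693/Kel (both documents).
- Repaglinide alone: t½ about 1 h, so Kel is about 0.693 per hour; absolute bioavailability 56% (Protocol 8.1.2).
- Size of the interaction: not given. Let g be the AUC0-inf ratio, Treatment B to Treatment A, over an assumed range.

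**Units**
- Protocol form: CL/F × Kel = (L/h) × (1/h) = L/h².
- SAP form: CL/F ÷ Kel = (L/h) ÷ (1/h) = L.

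Only the SAP form is a volume.

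**Numerical gap between the forms.** Protocol value ÷ SAP value = Kel². In hours this is 0.693² = 0.48. In minutes Kel = 0.693/60 = 0.01155 and Kel² is about 0.00013. The factor depends on the time unit because the two quantities have different dimensions. It is therefore not a measure of bias.

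**Treatment comparison.** The B/A ratio is unit-free, so it can be compared. Suppose LOXO-292 changes only clearance, with V and F fixed. Then CL/F and Kel are both divided by g, and t½ is multiplied by g.
- SAP form: (1/g) ÷ (1/g) = 1.
- Protocol form: (1/g) × (1/g) = 1/g².

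| g | t½ under B | SAP form, B/A | Protocol form, B/A |
|---|---|---|---|
| 0.5 | 0.5 h | 1.00 | 4.00 |
| 1.25 | 1.25 h | 1.00 | 0.64 |
| 1.5 | 1.5 h | 1.00 | 0.44 |
| 2 | 2 h | 1.00 | 0.25 |
| 3 | 3 h | 1.00 | 0.11 |

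**How far the fixed-F assumption matters.** Vz/F is V divided by F. If inhibition raised F from 0.56 to its ceiling of 1 with V unchanged, the correct formula would itself fall, to 0.56/1 = 0.56 of its value under Treatment A. If only F changed and Kel did not, both formulas would give 1/g (0.50 at g = 2). The ratio of 1.00 in the table therefore needs both V and F fixed.

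**What uses the formula.** The ANOVA, least-squares means, ratios and 90% intervals cover AUC0-t, AUC0-inf and Cmax only (Protocol 14.3.1.2 and 14.3.1.4; SAP 6.7.1). CL/F, Kel and t½ are calculated without Vz/F. Vz/F appears only in descriptive tables: SAP Table 11-2 and Tables 14.2.1.1.3 and 14.2.1.1.4. SAP Section 6.5 has the parameters calculated in Phoenix WinNonlin and defines them in its own tables, so the form planned for reporting is the one that gives 1.00 in the table above.

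**The case for a change.** The best case for a change is that the error is real, sits in the current protocol, and costs one line to correct. Amendment 1 did not touch Section 13.3.2. Someone who recomputed Vz/F from the protocol would not match the study report and would find nothing to explain why. Section 9.2 calls the parameter primary, Section 14.3 sends major changes of primary endpoint definitions to an amendment, and a general statement of alignment in SAP Section 8 gives the report's author no prompt to mention the correction.

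The discrepancy stands, and so does the fact that Section 8 is silent on it. The rest carries less weight. The list in Section 9.2 also contains AUC%extrap and Kel, so it reads as a list of everything calculated for repaglinide. Section 8.2.3 and the statistical sections confine the primary comparison to three exposure measures. Restoring Kel to the denominator of a descriptive parameter, in line with its own label as a volume, is hardly a major modification. A reader who did recompute from the protocol would get litres per hour squared for something called a volume, and would find the right formula in SAP Table 6.1.

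One further caution: the protocol text was read from PDF by a program, and the finding turns on where one bracket falls. As read, the expression is unambiguous, but a conversion fault cannot be wholly excluded.

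**Conclusion.** The protocol formula is wrong as written and the SAP formula is right. It is a clerical slip in a descriptive parameter, already corrected in the document that governs the calculation. The false changes in volume (B/A of 0.44, 0.25 or 0.11 for half-lives of 1.5, 2 or 3 h) assume fixed volume and bioavailability and an interaction size that the documents do not state. They would arise only if the analyst set SAP Table 6.1 aside and used the protocol's expression. Under the plan as it will be carried out, Vz/F is calculated correctly, and the effect on the primary comparison is nil. If Section 13.3.2 is reopened for another reason the bracket can be tidied, but the statistical plan needs no change on this account.

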13.3.3 Analytical Method

Samples will be analyzed for plasma repaglinide and LOXO-292 using validated bioanalytical methods. Samples from subjects to be assayed are specified in [Section 14.2](#).

13.4 Blood Volume Drawn for Study Assessments

Table 1: Blood Volume during the Study

Sample Type	Number of Time Points	Approximate Volume per Time Point [*] (mL)	Approximate Sample Volume Over Course of Study (mL)
Screening laboratory safety tests (including hematology, serum chemistry, coagulation, serology, FSH (for postmenopausal female subjects only) and serum pregnancy (for female subjects only))			
On-study hematology, serum chemistry, coagulation, and serum pregnancy ([when collected at the same time] for female subjects only)			
Blood for LOXO-292 and repaglinide			
Total Blood Volume (mL) →			CCI

* Represents the largest collection tube that may be used for this (a smaller tube may be used). One 4 mL tube will be used at each blood draw timepoint, including when LOXO-292 and repaglinide blood draw timepoints coincide on Day CCI.

** If additional safety or PK analysis is necessary to obtain sufficient plasma/serum for analysis, additional blood (including blood drawn for glucose monitoring finger sticks) may be obtained (up to a maximum of CCI).

14 STATISTICAL CONSIDERATIONS

Data will be handled and processed according to Celerion Standard Operating Procedures, which are written based on the principles of GCP.

14.1 Sample Size Determination

Based on in vitro data, it is anticipated that LOXO-292 may inhibit the CYP2C8 enzyme and therefore affect the repaglinide PK profile. Sixteen (16) subjects are considered sufficient to evaluate the magnitude of this interaction.

14.2 Population for Analyses

PK Population: Plasma samples from all subjects will be assayed even if the subjects do not complete the study. All subjects who comply sufficiently with the protocol and display an evaluable PK profile (e.g., exposure to treatment, availability of measurements and absence of major protocol violations) will be included in the statistical analyses.

Safety Population: All subjects who received at least one dose of either of the study drugs will be included in the safety evaluations.

14.3 Statistical Analyses

Detailed methodology for summary and statistical analyses of the data collected in this study will be documented in a Statistical Analysis Plan (SAP). The SAP will be prepared by Celerion and agreed upon with the Sponsor. This document may modify the plans outlined in the protocol; however, any major modifications of the primary endpoints definition and/or its analysis will also be reflected in a protocol amendment. Additional statistical analyses other than those described in this section may be performed if deemed appropriate.

14.3.1 Pharmacokinetic Analyses

14.3.1.1 Descriptive Statistics

Values will be calculated for the respective plasma concentrations and the PK parameters listed in [Section 13.3](#) for repaglinide and LOXO-292 using appropriate summary statistics to be fully outlined in the SAP.

14.3.1.2 Analysis of Variance

An ANOVA will be performed on the ln-transformed AUC0-t, AUC0-inf, and Cmax of repaglinide. The ANOVA model will include treatment as fixed effect and subject as the random effect. Each ANOVA will include calculation of least-squares means (LSMs), the difference between treatment LSMs, the standard error and 90% confidence intervals associated with this difference.

14.3.1.3 Steady State Analysis (Period 2 only)

A steady state analysis will be performed on the ln-transformed morning predose Ctrough concentrations for LOXO-292, on Days CCI, using Helmert contrasts (Maganti et al, 2008). Additional predose Ctrough may be used for the steady-state analysis to gather more information on steady-state attainment.

Helmert contrasts are constructed such that each time point is compared to the mean of the subsequent time point. Steady state is concluded at the time point where no more statistical difference can be observed. The contrasts will be:

Comparison 1: Ctrough Day

Comparison 2: Ctrough Day

Comparison 3: Ctrough Day

Comparison 4: Ctrough Day

Comparison 5: Ctrough Day

Comparison 6: Ctrough Day

Comparison 6: Ctrough Day

Comparison 7: Ctrough Day

14.3.1.4 Ratios and Confidence Intervals

Ratios of LSMs will be calculated using the exponentiation of the difference between treatment LSMs from the analyses on the ln-transformed repaglinide AUC0-t, AUC0-inf, and Cmax when repaglinide is coadministered with LOXO-292 (Treatment B) versus when administered alone (Treatment A). These ratios will be expressed as a percentage relative to the reference treatment (Treatment A).

Consistent with the two one-sided test (Schuirmann, 1987), 90% confidence interval (CIs) for the ratios will be derived by exponentiation of the CIs obtained for the difference between treatment LSMs resulting from the analyses on the ln-transformed repaglinide AUC0-t, AUC0-inf, and Cmax when repaglinide is coadministered with LOXO-292 (Treatment B) versus when administered alone (Treatment A). The CIs will be expressed as a percentage relative to the reference treatment (Treatment A).

